- Group 2: Joint Line Landmark Based (sham Ultrasound)
- Group 3: Suprapatellar Ultrasound Guided
- Group 4: Suprapatellar Landmark Based (sham Ultrasound)

The patients will be blinded to their group assignment prior to the first injection and will not be able to see which technique is employed. The provider performing the injections will not be blinded. The third injection (only) will be different in that contrast medium will be injected along with the hyaluronan. Following the third injection, fluoroscopy will be used to determine presence/absence of the contrast medium into the joint. The radiologist interpreting these images will be blinded to the technique employed. At 3 months following the third injection, the patients will be contacted by a surveyor blinded to the group assignment.

Objectives and Specific Aims

- 1. To compare the accuracy of injections into the knee joint with two different approaches, joint line and suprapatellar pouch
- 2. To determine if the addition of ultrasound guidance to traditional landmark-based techniques enhances the accuracy of these techniques
- 3. To examine differences in patient perceived pain and functioning of their knee joint following the injection series.

Medical Application

Injections into the knee joint are an exceedingly common procedure by a variety of specialists, primary care physicians, and non-physician clinicians. Knowledge of the most accurate and clinically effective injection technique will positively impact countless future patients. If we find that the addition of ultrasound guidance increases accuracy, as

we hypothesize, patient-oriented results should be better with fewer complications. This will allow the patient to return to activity quicker.

Background and Significance

Literature Review (as of 18 November 2010) and Preliminary Data and/or Findings.

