It is appropriate to use human subjects as research volunteers for this study. As this is a clinical trial, it would be impossible to do the study without human subjects. Due to the variation of ultrasound appearance and palpatory feedback used during an injection between live versus preserved tissue, it is not preferable to perform this trial on cadaveric subjects. Further, this study seeks patient oriented outcomes to further elucidate the applicability of these techniques. All of the techniques described above are currently used in clinical practice and will be recommended as part of the treatment plan per usual standard of care. As such, there are no additional risks associated with completion of this study other than reaction to the contrast agent.

Type of the Subject Population

Male and female subjects age 18 to 90 years presenting to a sports medicine clinic with knee pain justifying injection of a hyaluronic acid product will comprise the study population. The decision to use one of these products does not typically follow an algorithm that takes into account duration of symptoms or failure of modalities. Instead, this procedure is typically performed after the risks and benefits of various treatment options are discussed with the patient and he/she elects to receive this injection in concert with or as opposed to any number of other treatment modalities for knee osteoarthritis.

Inclusion and Exclusion Criteria

a. Inclusion Criteria

- 1. Male or female, age 18 to 90
- 2. Clinician determined need for intra-articular knee injection

b. Exclusion Criteria

- 1. Allergy to contrast dye, shellfish
- 2. Allergy to egg products or hyaluronate
- 3. Allergy to lidocaine
- 4. Localized skin infection at planned site of injection
- 5. Inability to complete follow-up phone call three months following the injection

Recruitment

Any adult-aged individual that meets inclusion and exclusion criteria will be eligible to participate in the study. Due to the expected large cohort of participants already present within the patient population at the trial site, no advertising will be necessary for this study.

Compensation for participation

No compensation will be provided to subjects.

Consent Process

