- **a.** There will be a Research Coordinator at the trial site who will administer the consent and HIPAA authorizations. This will be performed with a standardized consent form (Appendix A), including a scripted discussion of the study procedures and a scripted discussion of risks inherent in the injection techniques
- **b.** Upon completion of consent, the Coordinator will have the subject explain their understanding of the concept of treatment in their own words to ensure the subjects understand the consent.

Study Design

The study will be a randomized, double-blinded clinical study comparing four techniques for intra-articular knee injections.

The study investigators will receive a list of 120 computer generated random numbers from

Page 8 of 17 Version 2.0 one to four. No more than 30 will be in each group to ensure that each group is the correct size. Upon entry into the study, and prior to the first injection, subjects will randomized by selecting a sealed envelope from a box containing an equal number of envelopes for each of the four treatments groups. The envelope will be given, unopened, to the study doctor. The subject will be blinded to their study group assignment.

Double-blinding will be done as follows: The subjects will be blinded to whether ultrasound was used to guide their treatment. The radiologist, who will review the fluoroscopic images after the injections, will be blinded to treatment group assignment. The injecting physician will not be blinded to the treatment group assignment. Treating physicians (injecting physicians) will perform the technique as detailed below based on the assignment of the participant. Subjects and the radiologists will both be asked to guess their treatment group at each point in the data collection to determine the effectiveness of the blinding process. The Surveyor will also be blinded to the treatment group allocation.

The injecting physicians will consist of orthopedic surgeons, sports medicine fellows, or sports medicine fellowship trained primary care physicians. All injecting physicians will receive a minimum of 2 hours of hands-on training specific to the procedures employed in this study. Additionally, they will be supervised for their first several ultrasound-guided procedures to assure competence with the techniques.

Study Methodology/Procedures

Appointment 1

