Patients randomized to the Suprapatellar Landmark (SPL) group will receive the same procedure as the Suprapatellar Ultrasound Guided (SPUS) group., with the exception of the sham ultrasound. To accomplish this, the ultrasound probe will purposely be positioned in the transverse plane of the suprapatellar area but the ultrasound display will be positioned so that the patient cannot visualize the screen, and the "FREEZE" button will be activated so that no active image is transmitted. The display will be positioned such that visualization by the patient will not be possible. The injecting physician will insert the needle lateral to the vastus lateralis toward the suprapatellar pouch. When the injecting physician believes the needle tip is in the pouch, the viscosupplement will be injected followed by the contrast.

It should be noted, that none of the participants in the study will be given the ability to visualize the ultrasound screen or injection procedure.

- 5. Following each injection, all patients will conclude their encounter with the injecting physician by being asked to rate on a scale of 0 to 10 their procedural pain from the procedure. For pain, a score of 0 will correspond to no pain and 10 will correspond to the worst pain they have ever experienced. After each injection, and at the three month follow up telephone call, the subjects will be asked to rate their overall procedure satisfaction on a 0-10 scale where "0" represents complete dissatisfaction and "10" represents complete satisfaction.
- 6. After the third injection, and after answering these questions, the patient will proceed directly to the Radiology Department.
- 7. Images of the joint will be obtained following the third injection. These images will be analyzed by a radiologist blinded to the technique employed and used to determine presence of or absence of the contrast medium within the joint.

Appointment 4 (telephone)

8. Subjects will be contacted approximately three months after the procedure by a Surveyor and the WOMAC Osteoarthritis Index will be repeated. The patients will be asked to rate their procedural satisfaction and also detail other therapies they have employed since the injection. This will include supplements, exercise (frequency and duration), acupuncture, physical therapy, etc.

Data Collection

Data collection will occur at three points during the investigation:

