• Initial evaluation: Screening instrument for first visit (history and physical, diagnostic and inclusion/exclusion criteria), WOMAC (prior to receiving each of the three injections), and intervention

The clinical staff will collect the following data:

- Name, email, phone number
- Demographics: age, gender, type and number of injections received previously
- Informed consent/HIPAA document
- WOMAC Osteoarthritis Index
- Post Procedure

The Injecting physician will record the following data:

- Group Assignment
- Amount and type of therapeutic substance injected
- Total time to complete procedure from sterilization to bandaging
- Procedural Pain Score (0 to 10)
- Procedural Satisfaction Score (0 to 10)
- Complications

In a separate electronic database, the radiologist will record the following data:

- Name
- Presence or absence of contrast material within the knee joint
- Three months after intervention (telephone)
 - WOMAC Osteoarthritis Index
 - Procedure Satisfaction Score (0 to 10)

Study Time Line

Assessment					
Study Day /	Initial Evaluation	and	Second	Third Injection	3 months
Period	First Injection		Injection	With contrast	Post Treatment
Screening	Х				
Informed	Х				
Consent, discuss					
Plan, etc.					
Randomization	Х				
Demographics,	Х				
History &					
Physical					
WOMAC (pre	х		Х	Х	Х
injection)					
Treatment	X		Х	Х	
Procedural Pain	Х		Х	Х	
(post injection)					
Procedural	Х		Х	X	Х

Satisfaction (post injection)			
Fluoroscopic Analysis		Х	
Complications (post injection)		X	

Statistical Consideration

Primary endpoints are presence/absence of contrast medium in the joint, the WOMAC osteoarthritis index, and overall satisfaction with the injection technique. Our statistical analysis of the WOMAC index will consider a mean change from baseline to post-injection with the variables of pain, stiffness, and function. We will also study the mean change of the Global Score from the WOMAC.

Data Analysis

Statistical analysis of the WOMAC score will consist of one-way analysis of variance (ANOVA) followed by Tukey's post-hoc multiple comparisons between the four groups with a 5%, two-sided familywise significance level (which allows for comparisons between all possible pairs of treatments). Chi square tests will be used to compare the percent accuracy among the four groups. We will also perform sub-analysis to determine if any trends can be linked to the type of medication (viscosupplementation) injected versus accuracy.

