Safety Monitoring and Analysis Plan

Since treatments are provided at the onset of the study, "stopping rules" will not apply in this study. Since the primary outcome includes pain and functioning at baseline and 3 months following the intervention, the entire study must be carried out in order to gather the desired data. There have been no unexpected side effects other than local pain and swelling at the injection site that have been reported in the studies using these injection techniques, so we do not believe any other specific side effects will need to be monitored. Patients will not be included in the study if a contraindication applies to them. Of note, viscosupplementation is not contraindicated in pregnant patients.

Sample Size Estimation

For the comparison of accuracy, a two group chi square test with a 5% two-sided significance level will have 80% power to detect a difference of 33 percentage points between groups when the accuracy in the less-accurate condition is 60% and the sample size in each group is 25.

Previous studies have demonstrated an effect size of the WOMAC ranging from 0.5 to 1.0 when medication interventions were studies on patients with knee pain. A sample size of 25 in each group will have 80% power to detect an effect size of 0.809 using a two group t-test with a 5% two-sided significance level.

Reference: Lenth, R. V. (2006-9). Java Applets for Power and Sample Size [Computer software]. Retrieved November, 2010, from http://www.stat.uiowa.edu/~rlenth/Power.

Reporting Adverse Events

Definitions:

Adverse events (adverse effects, adverse reactions): any occurrence of injury, dysfunction, disease, or abnormality of any organ or tissue that occurs in a subject enrolled in a clinical protocol. Manifestations of an adverse event may include symptoms, physical exam abnormalities, diagnostic study abnormalities, and/or death.

Expected adverse events: adverse events previously known or anticipated to result from: 1) the interventions and interactions used in the research (these events must be included as potential risks in the consent form); 2) the collection of identifiable private information under research (these events must be included as potential risks in the consent form); 3) an underlying disease, disorder, or condition of the human subjects; and/or 4) other circumstances unrelated to the research or any underlying disease, disorder, or condition of the subject.

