Unexpected adverse events /Unanticipated problems: adverse events that 1) are not expected given the nature of the research procedures and the subject population being studied; and 2) suggest that the research places subjects or others at a greater risk of harm or discomfort related to the research than was previously known or recognized.

Serious adverse event: an adverse event that is fatal, life-threatening, permanently disabling, require inpatient hospitalization, or result in congenital anomalies/birth defect, overdose or cancer, or any other adverse event that, based on appropriate medical judgment, may jeopardize the subject's health and may require medical or surgical intervention to prevent one of the other outcomes listed above.

Expected Adverse Events from Research Risks and Reporting

- Rare but serious (Event Rate < 1%): infection at the site of injection; contrast dye allergic reaction.
- Likely (5% ≤ Event Rate < 10%): 8% incidence of pseudo-synovitis with the use of Synvisc® products.
- More likely (Event Rate ≥ 10%): bruising, swelling and increased pain at site of injection for several days to a few weeks.

Monitoring of adverse clinical events will be done during each of the two scheduled followup assessments. These will be managed as follows:

- Infection at injection site, or blood-borne infection: manage as clinically indicated based on assessment by physician.
- Contrast dye reaction: treat as clinically indicated based on severity.
- Pseudo-synovitis: NSAIDs, ice, compression, elevation.
- Bruising, swelling and increased pain at site of injection: treat with compression, ice, and prescribed pain medications (no NSAIDs), and patient reassurance that these resolve with time.

Reporting Serious and Unexpected Adverse Events to the IRB

Serious Adverse Events: The PI, within one working day, will report all serious adverse events (SAE) occurring in subjects enrolled in the study. This is accomplished by submitting an adverse event report memorandum to the IRB. Serious adverse events will be reported even if the PI believes that the adverse events are unrelated to the protocol.

Unexpected (but not serious) adverse events occurring in subjects enrolled in the study, in the opinion of the PI, are possibly related to participation in the protocol will be reported by the PI within 10 (ten) working days to the IRB using the same procedure.

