For all serious and/or unexpected adverse events, the PI will forward a copy of the adverse event report to IRB. A summary of all serious or unexpected side effects also will be included in the APR.

Protected Health Information

All participant PHI and study results will be located in a password protected spreadsheet on a computer. The radiologist will also maintain a password protected spreadsheet on his/her personal work computer with password protected access and will provide this data as requested to the Principle Investigator. The Principle Investigator will maintain a central file of all PI and data on a password protected spreadsheet on a computer with password protected access.

Research documents that contain PHI will be destroyed when the study results have been published in a medical journal. Non-PHI results will be maintained indefinitely in the possession of the PI.

Reporting Protocol Deviations

Any protocol deviations during the course of the study will be promptly reported to the IRB and sponsor if applicable, through the medical monitor of the protocol if applicable. Examples of deviations include but are not limited to variances from the treatment schedule for an individual patient, failure to use the most current consent form, and/or incomplete or lost records.

Reporting protocol deviation is accomplished by submitting a protocol deviation memorandum to the IRB.

Cost

The trial participants will not be charged any fees above the typical cost of their encounter with their physician and the cost of the injection of their medication. The expected cost of the Omnipaque 300 will be \$6.25 per injection, totaling \$750.00 for the entire study (\$6.25 x 120 participants). [name] will provide accomplishment and interpretation of the fluoroscopic images at no additional charge.

References

2. Arthritiscenter.com [Internet]. Arthritis Center of Connecticut. Available from: http://www.arthritiscenter.com/html/joint_injection.php.

3. Aafp.org [Internet]. American Family Physician. Available from: http://www.aafp.org/afp/2002/1015/p1497.html.

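### The human-use justification names contrast reaction as the only added risk, but the study also adds a fluoroscopy after the third injection, with no pregnancy question at that visit

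*Combined protocol and SAP*

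**What the plan says.** All places are in the combined protocol and SAP.

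- **Human Use Justification.** The injection techniques are already in clinical use, and from this the section concludes that "there are no additional risks associated with completion of this study other than reaction to the contrast agent".
- **Methodology/Technical Approach.** Contrast is added at the third injection only. "Following the third injection, fluoroscopy will be used to determine presence/absence of the contrast medium into the joint".
- **Study Methodology/Procedures, items 6 and 7.** "After the third injection, and after answering these questions, the patient will proceed directly to the Radiology Department". Images are taken there and read by a blinded radiologist.
- **Statistical Consideration.** "Primary endpoints are presence/absence of contrast medium in the joint", together with the WOMAC index and satisfaction.
- **Cost.** The radiology provider "will provide accomplishment and interpretation of the fluoroscopic images at no additional charge", listed next to a contrast budget for 120 participants.
- **Expected Adverse Events from Research Risks and Reporting.** The rare but serious events are "infection at the site of injection; contrast dye allergic reaction". Pseudo-synovitis, bruising, swelling and pain make up the rest of the list.
- **Consent Process.** The consent discussion has two scripted parts, one on the study procedures and "a scripted discussion of risks inherent in the injection techniques".
- **Inclusion and Exclusion Criteria.** Men and women aged 18 to 90 are eligible. None of the five exclusions concerns pregnancy.
- **Safety Monitoring and Analysis Plan.** Patients with a contraindication are not included. The section then notes that pregnancy does not rule out viscosupplementation.
- **Study Time Line.** Screening is scheduled at the first visit only.

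**The concern.** The risk statement is absolute, and its reasoning covers only the injections. If the techniques are usual care, they add no risk; the fluoroscopy is not part of that argument. It is done because the study needs to see where the contrast went, and it exposes the participant to X-rays. A reader relying on the human-use justification would conclude that the study adds no radiation.

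The pregnancy point follows from this and is secondary. A participant who becomes pregnant, or learns that she is, between screening and the third visit would receive research-only contrast and X-ray if the written steps were followed. At stake is the accuracy of a safety statement and a simple protection at one visit. The validity of the trial's comparisons is not affected.

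**Working it through.** **1. Is the fluoroscopy added by the study?** Contrast is given at the third injection only. The sole stated use of the images is to detect contrast in the joint, which is a primary endpoint. The images come without extra charge and are costed beside the study contrast. Nothing describes fluoroscopy as routine after a viscosupplement injection. The Human Use Justification already counts the contrast as added by the study, and the fluoroscopy exists only to read that contrast. So it is study-added.

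**2. Is the risk stated elsewhere?** The supplied text does not mention radiation. The expected-event list names contrast allergy and nothing from imaging. The risk part of the consent script is described in terms of the injection techniques. The script on study procedures may mention imaging, and the consent form is not in the supplied text, so nothing is concluded about what participants are told.

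**3. How many examinations?** At most 30 per group (Study Design), so 4 × 30 = 120. The contrast budget agrees: $6.25 × 120 = $750. If each group ends with the 25 readings used in Sample Size Estimation, the count is 4 × 25 = 100. Anyone who stops before the third injection is not imaged.

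**4. How long after screening?** Three injections about one week apart give two gaps of about 7 days, so imaging falls about 14 days after the first visit. All three must be completed within one month, which sets the upper limit.

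**5. What would a few missing readings cost?** Two-group chi-square test, two-sided 5%, p₁ = 0.60, p₂ = 0.60 + 0.33 = 0.93 (Sample Size Estimation), no continuity correction:

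- p̄ = (n₁p₁ + n₂p₂)/(n₁ + n₂)
- s₀ = √[p̄(1 − p̄)(1/n₁ + 1/n₂)]
- s₁ = √[p₁(1 − p₁)/n₁ + p₂(1 − p₂)/n₂]
- power = Φ[(p₂ − p₁ − 1.96 s₀)/s₁]

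The plan's own figure comes first. With 25 per group, p̄ = 0.765, s₀ = 0.1199 and s₁ = 0.1105, so power = Φ[(0.33 − 1.96 × 0.1199)/0.1105] = Φ(0.86) = 0.805. This matches the stated 80%.

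| Readings, 60% group | Readings, 93% group | Power |
|---|---|---|
| 25 | 25 | 0.805 |
| 30 | 30 | 0.874 |
| 27 | 30 | 0.858 |
| 30 | 27 | 0.852 |
| 25 | 30 | 0.845 |
| 30 | 25 | 0.835 |

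Each group can lose 5 of 30 readings (5/30 = 16.7%), for all reasons together, before it falls below 25. The counts of 3 and 5 missing are illustrations, because the documents give no number of pregnant participants.

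**The case against.** The strongest reply concedes the risk sentence and contests the rest.

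- **The adverse-event list.** It covers injuries and abnormalities, and an imaging exposure is not itself one of these. That is fair. The list is used here only to show that nothing elsewhere repairs the omission.
- **The consent rule.** Reporting Adverse Events says of expected events that "these events must be included as potential risks in the consent form". That governs events and the consent form; it does not govern the human-use justification. This also stands, and the point does not rely on that rule.
- **The pregnancy gap.** The population is mainly discussed in terms of knee osteoarthritis, the contraindication clause may already exclude a known pregnancy at entry, and Radiology may ask as routine. All of this may be true, and it keeps the gap small. But an entry clause cannot detect a pregnancy that begins or becomes known after entry. A question asked in Radiology also comes after the contrast has been injected, too late to withhold it. The remark clearing viscosupplementation follows directly after the contraindication clause, so a reader could take pregnancy as no bar to any study procedure.
- **The contrast-allergy exclusion.** It deals with contrast reaction, but with neither radiation nor pregnancy.
- **The dose to a knee may be small.** Probably so. But the sentence does not say small; it says there is no other added risk. The protocol does list contrast allergy at a rate below 1%, so rarity is not its reason for leaving a risk out.

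**Conclusion.** The concern holds as a minor safety correction that should be made. The risk sentence is wrong as written: up to 120 participants, or 100 at the powered number, would have one study-added fluoroscopy that it does not acknowledge. The missing pregnancy question at the third visit is a real but smaller gap, spanning about 14 days to one month between screening and imaging.

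The conclusion rests on the supplied protocol text and on fluoroscopy being X-ray imaging. It makes no claim about the consent form or local Radiology practice. The documents give neither the radiation dose nor the number of participants who might be pregnant, so neither is estimated. Endpoints, analyses and the stated power calculation are unchanged.

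**What to change.** 1. **Human Use Justification.** Replace the absolute statement with: *Study-added risks include reaction to the contrast agent and ionising radiation from one fluoroscopic examination of the knee after the third injection.*
2. **Safety Monitoring and Analysis Plan.** State that the contraindication clause applies to the contrast and the fluoroscopy as well as to the viscosupplement.
3. **Third visit.** Ask about pregnancy before contrast is given, and add a matching row to the Study Time Line. A participant who is or may be pregnant receives the third injection without contrast or imaging, and her accuracy reading is recorded as missing.

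The cost is two sentences, one question with its schedule row, and possibly a very few missing readings, which the margin of five per group can absorb provided losses for other reasons leave room.

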Real time ultrasound guidance using a standardized ultrasound unit with a 10 MHz linear array transducer (Logiq E ®, General Electric Healthcare, Chalfont St. Giles, United Kingdom) will be used to guide the injection for this group. The ultrasound display will be positioned so that the patient cannot visualize the screen. After sterile prep of the anteriolateral suprapatellar area (approximately 1 cm superior to the patella at a level approximating that of the lateral patellofemoral joint space), the suprapatellar pouch will be visualized. First, a longitudinal view capturing the proximal patella and the plane between the prefemoral fat pad (superficial to the femur) and suprapatellar fat pad (deep to the quadriceps tendon) will be obtained. Presence or absence of an effusion, visualized as a localized collection of anechoic material within this plane, will be noted. Next, the probe will be turned 90 degrees to a transverse view of the plane just proximal to the patella. Small adjustments in probe positioning will be done to create the best visualization of the suprapatellar pouch. After the desired visualization is achieved the needle will be inserted just lateral to the vastus lateralis in the longitudinal axis of the US probe and angled medially until the tip of the needle is within the suprapatellar pouch. Should an effusion be present, this will serve as the target landmark. In this instance, the effusion will be aspirated using a clean 5ml syringe prior to the injection. In the absence of an effusion, the target landmark will be the plane between the prefemoral and suprapatellar fat pads. In the absence of an effusion, injection of saline will be done first to dissect this plane further to assure that the needle tip is within the suprapatellar pouch. Once the injecting physician is confident of needle position with the pouch, the viscosupplement will be injected followed by the

contrast.

Group 4: Suprapatellar Landmark (SPL)

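### The written Group 4 sham does not reproduce the Group 3 probe routine, which may weaken patient blinding to guidance for WOMAC and satisfaction in the suprapatellar comparison

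*Combined protocol and SAP*

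**What the plan says.** The Study Design section states the aim: "The subjects will be blinded to whether ultrasound was used to guide their treatment".

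The Group 3 (SPUS) description sets out three probe steps before the needle goes in:
- It opens with one orientation: "First, a longitudinal view capturing the proximal patella and the plane between the prefemoral fat pad".
- It then changes orientation: "Next, the probe will be turned 90 degrees to a transverse view of the plane just proximal to the patella".
- It ends with finer movement on the skin: "Small adjustments in probe positioning will be done to create the best visualization of the suprapatellar pouch".

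The Group 4 (SPL) description says that these patients "will receive the same procedure as the Suprapatellar Ultrasound Guided (SPUS) group., with the exception of the sham ultrasound". It then defines the sham: "the ultrasound probe will purposely be positioned in the transverse plane of the suprapatellar area", with the image frozen and the display out of the patient's sight. It mentions no longitudinal view, turn or adjustment.

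The masking measures for patients concern sight. The text after the group descriptions adds that "none of the participants in the study will be given the ability to visualize the ultrasound screen or injection procedure". Study Design also plans a check on blinding: "Subjects and the radiologists will both be asked to guess their treatment group at each point in the data collection".

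Statistical Consideration names three primary endpoints: contrast in the joint, WOMAC, and satisfaction with the technique. The patient rates the last two.

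**The concern.** A sham protects blinding only if the patient's experience of it resembles the real procedure. Hiding the screen does not hide probe handling, because the patient can still sense where the probe is placed, whether it is turned and how long it is moved about. If Group 3 patients more often come to believe that they were guided than Group 4 patients do, expectation adds to the difference in their self-ratings and can pass for an effect of ultrasound.

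The comparison at stake is Group 3 v 4 on WOMAC and satisfaction, which serves Objective 3 (perceived pain and function). It is one of only two comparisons of guidance within a single approach. Satisfaction is the more exposed endpoint, because it is a rating of the technique itself and is taken after each of the three injections and again at three months.

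**Working it through.** **1. The two suprapatellar routines side by side**

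| Probe step | Group 3 (guided) | Group 4 (sham) |
|---|---|---|
| Longitudinal view | Yes, first | Not described |
| 90-degree turn | Yes | Not described |
| Transverse position | Yes | Yes |
| Small adjustments | Yes, to improve the view | Not described |
| Image | Live | Frozen |

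The equivalence sentence does not fill the gaps in the right-hand column. It makes the sham ultrasound the exception and then defines it without those steps. With a frozen image the operator, who is not blinded, has no imaging reason to add them.

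**2. The joint-line pair for contrast.** Groups 1 and 2 both have the probe placed obliquely on the soft tissue triangle opposite the injection site. The mismatch in described probe placement is therefore confined to Groups 3 and 4.

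**3. Which endpoints it can reach.** Contrast in the joint is judged by a radiologist blinded to technique, so patient belief does not enter. WOMAC and satisfaction are self-rated.

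**4. The plan's own figure.** Sample Size Estimation gives 80% power for an effect size of 0.809 with 25 per group (two-sided 5% t-test). The noncentral t distribution gives 80.0%, so the figure reproduces. It is not in dispute.

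**5. Illustration of size.** The documents give no figure for either input, so both are assumptions:
- the share believing they were guided differs between Groups 3 and 4 by 20 to 50 percentage points;
- that belief shifts a self-rating by 0.3 to 0.5 SD.

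Bias = difference in belief × shift:
- low: 0.20 × 0.3 = 0.06 SD
- high: 0.50 × 0.5 = 0.25 SD

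The randomization list allows 30 per group. Non-centrality = bias × √(30/2) = bias × 3.873:
- low: 0.06 × 3.873 = 0.23
- high: 0.25 × 3.873 = 0.97

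Rejection rate for Group 3 v 4 with no true effect:

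| Test | No bias | 0.06 SD | 0.25 SD |
|---|---|---|---|
| Tukey pair, four groups, df = 4 × 29 = 116, critical t = 2.61 (planned for WOMAC) | 1.0% | 1.2% | 5.4% |
| Single unadjusted 5% test, normal approximation, P(\|Z\| > 1.96) | 5.0% | 5.6% | 16.2% |
| Single unadjusted 5% t-test, df = 58 | 5.0% | 5.6% | 15.9% |

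Data Analysis specifies ANOVA with Tukey for WOMAC and chi-square for accuracy. It names no test for satisfaction, so for that endpoint the unadjusted rows are an assumption about the test as well as about the bias. Tukey's adjustment lowers the rejection rate but leaves the bias in the estimated difference.

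**6. The planned check.** Study Design asks for treatment guesses. The Data Collection lists and the study time line contain no item for them, and Data Analysis contains no analysis of them.

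**The case against.** The strongest reply is that the documents do not show that patients can tell the routines apart. Each patient is randomized once and is assigned one technique for all three visits, so nobody in the trial experiences both. A Group 4 patient would have to recognise a lone transverse placement as a sham with nothing to compare it with, and feeling a probe is not the same as knowing whether its image was live. This stands, and it is why the point says may weaken. It does not dispose of the point. Patients need no side-by-side comparison to form different beliefs, since a probe moved about until a view is found may suggest guidance more than a single placement does. Data Collection also records previous injections, so some patients may have a reference.

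A reader might infer that the sham probe is held still. The Group 4 text does not say so; it is silent on movement. The defect is that silence: operators may copy the scan, but nothing asks them to.

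A reader might also infer that the accuracy result, and so Objective 2, is compromised. It is not, because that objective concerns accuracy alone and the images are read blind.

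The treatment guess is a real safeguard and addresses exactly this risk. It would measure a loss of blinding but not prevent one, and as written it has no data field and no analysis.

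Finally, the probe may not be the strongest cue. The guided arms are described with a saline injection (Group 1) or with aspiration or saline (Group 3). The sham descriptions do not clearly include or exclude these steps. This stands as a separate issue, and it limits what a change to probe handling alone can achieve.

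**Conclusion.** The point holds as a gap in the written sham. Followed as written, the plan leaves probe handling unmatched between Groups 3 and 4, masks patients only visually, and relies on patient ratings for two of its three primary endpoints. That may weaken blinding to guidance and bias the Group 3 v 4 comparison of WOMAC and satisfaction. That patients will in fact notice, or that blinding has failed, is not established.

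The size is unknown. Under the assumed biases the increase in false-positive rate is small to moderate for WOMAC under the planned Tukey test. It is larger for satisfaction if that endpoint is tested without adjustment. The 16% figure should not be read as applying to the planned WOMAC analysis. The change is worth making because it is cheap and because lost blinding cannot be repaired once the ratings have been collected.

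**What to change.** 1. In the Group 4 (SPL) description, state that the sham copies the Group 3 probe sequence with the display frozen throughout: longitudinal placement, 90-degree turn, and a brief set period of small adjustments before needle entry. The frozen image gives the operator no guidance, and the needle technique is unchanged.
2. Add the treatment guess to the Data Collection lists and the time line, and state an analysis by arm, such as a blinding index for each group.
3. Reconcile the group descriptions on whether Group 4 receives the saline and aspiration steps described for Group 3. Item 1 does not remove these as possible cues.

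The cost is protocol wording, one data field, and roughly a minute more per Group 4 injection, with no extra staff, equipment or patients. One side effect should be noted. Total procedure time is recorded from sterilization to bandaging, so Group 4 times would include the longer sham. No analysis of procedure time is planned.
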